## **7.1 DEMOGRAPHIC AND OTHER BASELINE CHARACTERISTICS**

Only descriptive statistics are planned for this section of the CTR. These will be based on the TS.

## **7.2 CONCOMITANT DISEASES AND MEDICATION**

Concomitant diseases will be coded according to the most recent version of MedDRA. Concomitant medication will be coded according to the most recent version of the World Health Organisation – Drug Dictionary. Concomitant non-drug therapies will be coded according to the most recent version of MedDRA.

Only descriptive statistics are planned for this section of the CTR.

**CTP Section 7.3.4:** *Previous and concomitant therapies will be presented per treatment group without consideration of time intervals and treatment periods.*

A medication will be considered concomitant to a treatment period, if it

- is ongoing at the time of study drug administration, or
- starts within the analysis phase of the respective treatment (see [Section 6.1](#) for a definition of treatments and analysis phases).

The relevance of the concomitant therapies to the evaluation of PK will be decided no later than at the RPM.

## **7.4 PRIMARY ENDPOINTS**

### **7.4.1 Primary analysis of the primary endpoints**

**CTP Section 7.3.1:** *The statistical model used for the analysis of the primary endpoints will be an analysis of variance (ANOVA) model on the logarithmic scale. That is, the PK endpoints will be log-transformed (natural logarithm) prior to fitting the ANOVA model. This model will include effects accounting for the following sources of variation: subjects and treatment. The effect 'subjects' will be considered as random, whereas the other effects will be considered as fixed. The model is described by the following equation:*

$$y_{km} = \mu + s_m + \tau_k + e_{km}, \text{ where}$$

$y_{km}$  = logarithm of response measured on subject  $m$  receiving treatment  $k$ ,  
 $\mu$  = the overall mean,

$s_m$  = the effect associated with the  $m^{th}$  subject,  $m=1,2,\dots,n$   
 $\tau_k$  = the  $k^{th}$  treatment effect,  $k = 1, 2$   
 $e_{km}$  = the random error associated with the  $m^{th}$  subject who received treatment  $k$ ,

where  $s_m \sim N(0, \sigma_B^2)$  i.i.d.,  $e_{km} \sim N(0, \sigma_W^2)$  i.i.d. and  $s_m, e_{km}$  are independent random variables.

Point estimates for the ratios of the geometric means (test/reference) for the primary endpoints (see Section 2.1) and their two-sided 90% confidence intervals (CIs) will be provided.

For each endpoint, the difference between the expected means for  $\log(T)$ - $\log(R)$  will be estimated by the difference in the corresponding adjusted means (Least Squares Means). Additionally their two-sided 90% confidence intervals will be calculated based on the residual error from the ANOVA and quantiles from the t-distribution. These quantities will then be back-transformed to the original scale to provide the point estimate and 90% CIs for each endpoint.

The analysis of primary endpoints will be based on the PKS.

#### Exclusion of PK parameters

The ADS ADPP contains column variables APEXC and APEXCO indicating inclusion/exclusion (APEXC) of a PK parameter and an analysis flag comment (APEXCO). All analyses based on the PKS are based on PK parameter values which are not flagged for exclusion, i.e. with APEXC equal to "Included".

**CTP Section 7.3:** *Plasma concentration data and parameters of a subject will be included in the statistical pharmacokinetic (PK) analyses if they are not flagged for exclusion due to a protocol deviation relevant to the evaluation of PK (to be decided no later than in the Report Planning Meeting) or due to PK non-evaluability (as revealed during data analysis, based on the criteria specified below). Exclusion of a subject's data will be documented in the CTR.*

#### Exclusion of plasma concentrations

The ADS ADPC (PK concentrations per time-point or per time-interval) contains column variables ACEXC or ACEXCO indicating inclusion/exclusion (ACEXC) of a concentration and an analysis flag comment (ACEXCO). Exclusion of a concentration depends on the analysis flag comment ACEXCO. For example, if ACEXCO is set to "ALL CALC", the value will be excluded for all types of analyses based on concentrations. If ACEXCO is set to "DESC STATS" the value will be excluded from descriptive evaluations per planned time point/time interval. If ACEXCO contains the addition "TIME VIOLATION" or "TIME DEVIATION", the value can be used for further analyses based on actual times. If ACEXCO is set to "HALF LIFE", the value will be excluded from half-life calculation only; the value is included for all other analyses. Excluded concentration itself will be listed in the CTR associated with an appropriate flag.

Further details are given in “Noncompartmental Pharmacokinetic/Pharmacodynamic Analyses of Clinical Studies” [\(4\)](#) and “Description of Analytical Transfer Files and PK/PD Data Files” [\(5\)](#).

#### **7.4.2        Further exploratory analyses of the primary endpoints**

**CTP Section 7.3.1:** *The same statistical model as stated above will be repeated for the primary endpoints but with 'subjects' considered as fixed effect.*

**CTP Section 7.3.1:** *In addition to the model based approach all parameters will be calculated and analysed descriptively.*

The analysis of primary endpoints will be based on the PKS.

### **7.5        SECONDARY ENDPOINTS**

#### **7.5.1        Key secondary endpoints**

This section is not applicable as no key secondary endpoint has been specified in the protocol.

#### **7.5.2        Secondary endpoints**

The analysis of secondary endpoints will be based on the PKS.

[figure not shown]
##### **7.5.2.1        Secondary endpoint analysis**

**CTP Section 7.3.2:** *The secondary endpoints (refer to Section 2.1.3) will be calculated according to the relevant BI internal procedures and will be assessed statistically using the same methods as described for the primary endpoints.*

Exclusion of PK parameter and exclusion of plasma concentrations are handled as described in [Section 7.4.1](#).

#### **7.6.1        Safety parameters**

Safety endpoints and tolerability will be analysed as described in [Section 7.8](#) of this TSAP.

## **7.8 SAFETY ANALYSIS**

All safety analyses will be performed on the TS.

**CTP Section 7.3.4:** *For all analysis, the treatment actually administered (= treatment at onset) to the subject will be used.*

### **7.8.1 Adverse Events**

AEs will be coded with the most recent version of MedDRA.

The analyses of AEs will be descriptive in nature. All analyses of AEs will be based on the number of subjects with AEs and not on the number of AEs.

For further details on summarization of AE data, please refer to "Analysis and Presentation of Adverse Event Data from Clinical Trials" [\(7\)](#) and "Handling of missing and incomplete AE dates" [\(3\)](#).

The analysis of AEs will be based on the concept of treatment emergent AEs. That means that all AEs will be assigned to screening or on-treatment periods as defined in [Section 6.1](#). AEs will be analysed based on actual treatments, as defined in [Table 6.1: 1](#).

An overall summary of AEs will be presented. This overall summary will comprise summary statistics for the class of AESIs.

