On treatment	BI 1358894 + Bupropion		Date/time of administration of Bupropion at Day 1, Visit 3	Date/time of administration of Bupropion (Visit 3) + REP (5 days * 24 h) or 12:00 a.m. on day after subject's end of trial termination date, whichever occurs earlier.
On treatment	BI 1358894		Date/time of administration of Bupropion (Visit 3) + REP (5 days * 24 h)	Date/time of last administration of BI 1358894 + REP (14 days * 24 h) or 12:00 a.m. on day after subject's end of trial termination date, whichever occurs earlier.
Follow-up	F/U BI 1358894		Date/time of last administration of BI 1358894 + REP (14 days * 24 h)	12:00 a.m. on day after trial termination date

 See [Section 6.7](#) for definition of baseline, which will be used in the statistical analyses of safety laboratory data and vital signs.

AE summary tables will present results for the on-treatment phase only. All AEs will be listed.

**CTP Section 7.3.4:** Note that AEs occurring after the last per protocol contact but entered before final database lock will be reported to Pharmacovigilance only and will not be captured in the trial database.

The following AE tables will be provided in the report:

- Section 15.3, Appendix 16.1.13.1.8.1 and 16.1.13.1.8.2 of the CTR displays

In these displays, the on-treatment phase will be analysed (labelled with the name of the study treatment (short label)). Screening will not be included in this analysis.

In Section 15 AE tables (but not in Appendix 16.1.13.1.8.1 and Appendix 16.1.13.1.8.2 AE tables), the following totals will be provided in addition:

- "Total Bupropion", defined as the total over all on-treatment phases involving bupropion
- "Total BI", defined as the total over all on-treatment phases involving BI
- "Total on-trt", defined as the total over all on-treatment phases involving BI and bupropion

Listings of AEs presented in Section 15.4 will display results for the screening, on-treatment phases, and follow-up phases (labelled with the name of the study treatment (short label)).

Safety laboratory data and vital signs will be analyzed based on treatments in the respective treatment period (Period R: Bupropion; Period T: BI + Bupropion) with clear differentiation between baseline (cf. [Section 6.7](#)) and on-treatment measurements. Measurements will be considered on-treatment, if they were taken within the on-treatment phases as defined in [Table 6.1: 1](#).

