More details on the technical implementation of these analyses are provided in the ADS Plan of this TSAP.

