### **6.3 SUBJECT SETS ANALYSED**

The treated set (TS) and pharmacokinetic parameter analysis set (PKS) will be used as defined in the CTP, Section 7.3.

Table 6.3: 1 Subject sets analyzed

Class of endpoint	Subject set	
	TS	PKS
Disposition	X	
iPDs	X	
Primary PK endpoints		X
Secondary PK endpoint		X
Further PK endpoints		X
Safety parameters	X	
Demographic/baseline characteristics	X	
Treatment exposure	X	

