## 7. PLANNED ANALYSIS

The format of the listings and tables will follow the BI guideline "Reporting of clinical trials and project summaries" [\(6\)](#).

The individual values of all subjects will be listed. Listings will be sorted by subject number, visit and time point (if visit/ time point is applicable in the respective listing). AE listings will be sorted by assigned treatment (see [Section 7.8.1](#) below for details). The listings will be contained in Appendix 16.2 (SDL) of the CTR.

The following standard descriptive statistical parameters will be displayed in summary tables of continuous variables:

N	number of non-missing observations
Mean	arithmetic mean
SD	standard deviation
Min	minimum
Median	median
Max	maximum

For plasma concentrations as well as for all PK parameters the following descriptive statistics will additionally be calculated:

CV	arithmetic coefficient of variation
gMean	geometric mean
gCV	geometric coefficient of variation

For PK parameters the following descriptive statistics will additionally be calculated:

P10	10 th percentile
Q1	1 st quartile
Q3	3 rd quartile
P90	90 th percentile

The data format for descriptive statistics of plasma concentrations will be identical with the data format of the respective concentrations. The descriptive statistics of PK parameters will be calculated using the individual values with the number of decimal places as provided by the evaluation program. Then the individual values as well as the descriptive statistics will be reported with three significant digits in the CTR.

Tabulations of frequencies for categorical data will include all possible categories and will display the number of observations in a category as well as the percentage (%) relative to the respective treatment group. Percentages will be rounded to one decimal place. The category missing will be displayed if and only if there actually are missing values. Percentages will be based on all subjects in the respective subject set whether they have non-missing values or not.

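### Do two phases sharing the label 'BI 1358894', with windows of unequal length, make the adverse event tables misleading?

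*SAP*

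**What the plan says.** SAP Section 6.1 cuts each subject's time into analysis phases. Table 6.1: 1 has four on-treatment rows, and two of them are labelled 'BI 1358894'. The first runs from the first BI 1358894 dose to the Visit 3 bupropion dose, with an earlier end for a subject who stops BI 1358894 before that. The second runs from the Visit 3 bupropion dose plus 5 days to "Date/time of last administration of BI 1358894 + REP (14 days * 24 h"), unless the trial ends sooner for that subject.

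The AE displays follow these rows. Section 7.8.1 says "AEs will be analysed based on actual treatments, as defined in" that table, and Section 6.1 adds "In these displays, the on-treatment phase will be analysed (labelled with the name of the study treatment (short label")). It also adds totals, among them 'Total Bupropion', "defined as the total over all on-treatment phases involving bupropion", and a matching 'Total BI'.

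The unit is the subject ("All analyses of AEs will be based on the number of subjects with AEs and not on the number of AEs"), and Section 7 sets the denominator: "Percentages will be based on all subjects in the respective subject set whether they have non-missing values or not".

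Two pointers lead to material that is not in view. Table 6.3: 1 lists "Treatment exposure" as an output on the treated set, and Section 6.1 closes with "More details on the technical implementation of these analyses are provided in the ADS Plan of this TSAP". Section 7.8.1 also refers to a sponsor standard for how AE data are summarised.

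**The concern.** One label covers two different stretches of time: one with a dose every day, one with none. If the phases are merged by label, a single column mixes them. The visible text does not say whether they are merged.

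A percentage of subjects with at least one AE also takes no account of time at risk. Protocol Section 7.3.4 says treatments will be compared descriptively, and a reader may set the BI 1358894 column beside the bupropion column. With no drug effect at all, the longer window would be expected to show the higher percentage. BI 1358894 could then look less well tolerated than it is, in the trial report and in the registry tables drawn from it.

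**Working it through.** Hours are relative to the Visit 3 bupropion dose (Day 1 = 0 h; the flow chart has no Day 0), for a subject who completes as planned.

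**The plan's own figures.** Days -14 to -1 give 14 doses and Days 1 to 5 give 5, so 14 + 5 = 19, as stated. 19 x 100 mg = 1900 mg, as in protocol Table 4.1.4: 1. Day 1 is dose 14 + 1 = 15, as stated. The last dose is at 96 h, and 96 + 14 x 24 = 432 h, which is Day 432/24 + 1 = 19. That is the earliest end-of-trial day in flow chart footnote 10.

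**Phase lengths**, from the start and end rules in Table 6.1: 1, with AE questionings counted from the flow chart after the dose that opens the phase:

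| Phase | From | To | Days | BI doses | AE questionings |
|---|---|---|---|---|---|
| Bupropion (Period R) | own dose, 0 h | 120 h | 5 | 0 | 7 |
| BI 1358894, before bupropion | -336 h | 0 h | 14 | 14 | 14 |
| BI 1358894 + Bupropion | 0 h | 120 h | 5 | 5 | 7 |
| BI 1358894, after bupropion REP | 120 h | 432 h | 13 | 0 | none strictly inside; Day 6 at its start, Day 19 at its end |

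A column formed by label spans 14 + 13 = 27 days. 'Total Bupropion' spans 5 + 5 = 10 days and 'Total BI' 14 + 5 + 13 = 32 days.

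**What length alone could do.** The documents give no AE rate, so this is an assumption: a constant background hazard, no drug effect, and a fraction p of subjects with an AE in 5 days. Then P(d) = 1 - (1 - p)^(d/5).

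| p (5 days) | 14 days | 27 days |
|---|---|---|
| 5% | 13.4% | 24.2% |
| 10% | 25.5% | 43.4% |
| 20% | 46.5% | 70.0% |

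At p = 10% and 18 subjects this is 18 x 0.10 = 1.8 against 18 x 0.255 = 4.6 or 18 x 0.434 = 7.8 subjects. The direction is as feared, but the size comes wholly from the assumed p.

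**What the layout decides.** Merging or separating the two rows changes only the BI 1358894 column or columns. The Bupropion and BI 1358894 + Bupropion columns stay as they are. 'Total BI' is the union of the same three phases either way, so its count does not move.

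**Whether the second phase belongs under this label.** Protocol Section 7.3.4 assigns time up to the end of the REP to treatment, and Section 1.2.3 sets 14 days for BI 1358894 from an effective half-life of 50 to 70 h. The second phase opens 24 h after the last dose. With simple exponential decline, the level is then 2^(-24/50) = 72% to 2^(-24/70) = 79% of that at the last dose. The phase lasts 432 - 120 = 312 h, or 312/70 = 4.5 to 312/50 = 6.2 half-lives. BI 1358894 is therefore still present for much of it.

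Table 6.1: 1 uses the same convention elsewhere. The Bupropion row is one dose followed by residual days. The first BI 1358894 row already takes in residual days for a subject who stops early.

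**The case for a change.** The best case for a change starts from protocol Section 7.3.4, which leaves the detailed definition of treatment assignments and intervals to the SAP. A repeated label with no rule on columns leaves that job slightly unfinished. The registry tables show non-serious AEs above 5% by treatment; in a column of 18, one subject is 1/18 = 5.6%, so longer windows put more preferred terms under BI 1358894. Questioning is daily in the first BI phase and absent inside the second. Distinct labels and a row of subject-days would cost almost nothing.

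Part of this stands. The label is repeated, the visible text is silent on columns, and windows of 14 or 27 days against 5 are unequal.

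The rest is weaker:

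- The intervals are defined to the hour. Only the column layout is open, and the ADS Plan or the AE standard may settle it.
- The public SAP passes from Section 7.6.1 to 7.8, and its listed exposure output is described nowhere in view. That fits a removed exposure section, so it cannot be said that durations go unreported.
- The 5% threshold filters nothing in any full column of 18, bupropion included. Terms shown under BI 1358894 are events that began in that phase.
- AEs are recorded throughout and subjects must report them spontaneously (flow chart footnote 7; protocol Section 5.2.6.2.1). The Day 19 questioning looks back over the second phase.
- No text sets 'Total BI' against 'Total Bupropion'. Both contain the combination phase in the same subjects, so they are not natural comparison groups.
- Rates per subject-day would not make BI 1358894 and bupropion alone comparable. Bupropion alone always comes first (protocol Section 4.1.3), so period and treatment stay confounded.

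**Conclusion.** No change is needed. The repeated label is a small gap that whoever programs the tables will settle one way or the other. The unequal windows follow from a single-dose probe given with a 19-day perpetrator that has a 14-day REP. Subject counts by phase are correct as specified, and all AEs are also listed, with the listings in report Section 15.4 covering screening, on-treatment and follow-up phases. In 18 subjects a reader can inspect every case.

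The reach is narrow: descriptive BI 1358894 percentages over 14 or 27 days beside bupropion-alone percentages over 5. The contrast that answers the trial's question is 5 against 5 days with 7 against 7 scheduled questionings, and the PK analysis does not use these phases. Relabelling, or printing lengths that can be derived from Table 6.1: 1, would make the tables tidier without altering a result or conclusion.

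This rests on completers following the planned schedule (early stopping changes the lengths), on the flow chart as printed, and on AE tables being read as descriptions of each phase rather than as a test between drugs.

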**CTP Section 5.2.6.1.4: The following are considered as AESIs:**

- **Hepatic injury**  
*A hepatic injury is defined by the following alterations of hepatic laboratory parameters:*
  - *An elevation of AST (aspartate transaminase) and/or ALT (alanine transaminase)  $\geq 3$  fold ULN combined with an elevation of total bilirubin  $\geq 2$  fold ULN measured in the same blood sample, or*
  - *Aminotransferase (ALT, and/or AST) elevations  $\geq 10$  fold ULN*

The investigator had to classify on the eCRF whether an observed AE was an AESI or not.

According to ICH E3 [\(8\)](#), in addition to Deaths and Serious Adverse Events, 'other significant' AEs need to be listed in the clinical trial report. These will be any non-serious adverse event that led to an action taken with study drug (e.g. discontinuation or dose reduced or interrupted).

The frequency of subjects with AEs will be summarised by treatment, primary SOC and preferred term. AEs which were considered by the investigator to be drug related will be summarised separately. Separate tables will also be provided for subjects with SAEs and subjects with AESIs. AEs will also be summarized by maximum intensity.

The SOCs and preferred terms within SOCs will be sorted by descending frequency over all treatment groups.

For disclosure of AE data on ClinicalTrials.gov, the frequency of subjects with non-serious AEs occurring with an incidence of greater than 5 % (in preferred terms) will be summarised by treatment, primary SOC and preferred term. The frequency of subjects with SAEs will also be summarised.

For disclosure of AE data in the EudraCT register, the frequency of AEs, the frequency of non-serious AEs with an incidence of greater than 5 % (in preferred terms) and the frequency of SAEs will be summarized.

For support of lay summaries, the frequency of subjects with drug-related SAEs will be summarized by treatment, primary SOC and preferred term.

## **7.8.2      Laboratory data**

The analyses of laboratory data will be descriptive in nature and will be based on BI standards "Display and Analysis of Laboratory Data" [\(9\)](#).

Analyses will be based on normalised values, which means transforming to a standard unit and a standard reference range. The original values will be analysed if the transformation into standard unit is not possible for a parameter.

Descriptive statistics of laboratory values over time and for the difference from baseline (see [Section 6.7](#)) will be provided. Frequency tables of changes between baseline and last value on treatment with respect to the reference range will be presented by treatment.

Unscheduled measurements of laboratory data will be assumed to be repeat measurements of the most recent scheduled measurement (e.g. for follow-up or confirmation of a particular value). Therefore, unscheduled measurements will be assigned to the planned time point of the previous scheduled measurement. Descriptive statistics will be calculated by planned time point based on the worst value of the subject at that planned time point (or assigned to that planned time point).

Clinically significant abnormal laboratory values are only those identified either in the Investigator's comments or at the Report Planning Meeting at the latest. It is the Investigator's responsibility to decide whether a lab value is clinically significant abnormal or not.

Laboratory data will be compared to their reference ranges. Values outside the reference range as well as possibly clinically significant values will be highlighted in the listings. Possibly clinically significant laboratory values will be listed in Section 15.4.1.

Clinically relevant findings in laboratory data will be reported as baseline conditions (prior to first administration of study treatment) or as AEs (after first administration of study treatment) if judged clinically relevant by the investigator, and will be analyzed as such.

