Proprietary confidential information © 2021 Boehringer Ingelheim International GmbH or one or more of its affiliated companies

| Visit | Day | Planned Time [h:min] relative to Bupropion | Approximate clock time of actual day ¹ [h:min] | Event and comment | PK _(plasma) for BI 1358894 ⁶ | Clinical laboratory tests ² | PK _(plasma) for Bupropion and metabolites ⁶ | Vital signs (BP, PR) ECG ³ | Physical/Neurological Examination | Questioning for AEs and concomitant therapy ⁷ |
|-------|-----|--|---|---|--|--|---|---------------------------------------|-----------------------------------|--|
| 3 | -4 | -96:00 | 08:00 | Ambulatory visit Administration of 100 mg BI 1358894⁴ | X ¹⁵ | | | | | X |
| | -3 | -72:00 | 08:00 | Ambulatory visit Administration of 100 mg BI 1358894⁴ | X ¹⁵ | | | | | X |
| | -2 | -48:00 | 08:00 | Ambulatory visit Administration of 100 mg BI 1358894⁴ | X ¹⁵ | | | | | X |
| | -1 | -24:00 | 08:00 | Admission to trial site Administration of 100 mg BI 1358894⁴ | X ¹⁵ | B ¹² | | | X | X |
| | 1 | -0:30 | 07:30 | | X | | X | X | | X |
| | | 0:00 | 08:00 | Administration of 150 mg Bupropion⁴ and Administration of 100 mg BI 1358894⁴ | | | | | | |
| | | 1:00 | 09:00 | | | | X | | | |
| | | 2:00 | 10:00 | 240 mL fluid intake | | | X | | | |
| | | 3:00 | 11:00 | | | | X | | | |
| | | 4:00 | 12:00 | 240 mL fluid intake, thereafter Lunch ⁸ | | | X | | | X |
| | | 5:00 | 13:00 | | | | X | | | |
| | | 6:00 | 14:00 | | | | X | | | |
| | | 7:00 | 15:00 | | | | X | | | |
| | | 8:00 | 16:00 | Snack (voluntary) ⁸ | | | X | | | |
| | | 10:00 | 18:00 | | | | X | | | X |
| | | 11:00 | 19:00 | Dinner | | | | | | |
| | | 12:00 | 20:00 | | | | X | | | X |
| | 2 | 24:00 | 08:00 | Administration of 100 mg BI 1358894⁴ Discharge | X ¹⁵ | | X | X | X | |

Proprietary confidential information © 2021 Boehringer Ingelheim International GmbH or one or more of its affiliated companies

| Visit | Day | Planned Time [h:min] relative to Bupropion | Approximate clock time of actual day ¹ [h:min] | Event and comment | PK _(plasma) for BI 1358894 ⁶ | Clinical laboratory tests ² | PK _(plasma) for Bupropion and metabolites ⁶ | Vital signs (BP, PR) ECG ³ | Physical/Neurological Examination | Questioning for AEs and concomitant therapy ⁷ |
|-------|-----|--|---|--|--|--|---|---------------------------------------|-----------------------------------|--|
| | 3 | 48:00 | 08:00 | Ambulatory visit Administration of 100 mg BI 1358894⁴ | X ¹⁵ | | X | | | X |

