Because psychoactive drugs may impair thinking, judgment, and/or motor skills, participants should be cautioned about operating machinery, including automobiles, until they are reasonably certain that the study medication does not adversely affect their ability to engage in such activities. It is recommended that participants should exercise caution when driving or operating machinery.

Participants will be closely monitored during the trial participation (including safety laboratory, AE monitoring, physical and neurological examinations) to ensure that any occurring events are detected and any necessary actions taken.

BI 1358894 is a highly specific inhibitor of TRPC 4/5 channels, which are predominantly located in the CNS. All investigation into distribution and function of TRPC 4/5 (preclinical and clinical) so far have not identified any interference with the immune system, the respiratory system or the cardio-vascular system.

Therefore, no undue risk is expected from the multiple dose administration of 100 mg BI 1358894 over 19 days to healthy subjects planned for this trial.

Risks related to bupropion administration

The dose of bupropion administered in the current trial (two single doses of 150 mg extended release tablets separated by a bupropion free interval of 21 days) corresponds to the starting dose given in therapy. AEs will be appropriately monitored and could be adequately treated if necessary because the subjects will be hospitalized at the trial site under close medical surveillance for 24 h after bupropion administration. Subjects with contraindications for the use of bupropion will be excluded from participation (see Section [3](#)).

Single doses of 150 mg bupropion have been well tolerated by healthy volunteers in previous DDI trials. Due to the supposed CYP2B6 induction mediated by BI 1358894, plasma concentrations of bupropion and its metabolites may be decreased. Thus no undue risk is expected to healthy subjects from the combined administration of BI 1358894 and bupropion in this trial.

Although rare, a potential for drug-induced liver injury (DILI) is under constant surveillance by sponsors and regulators. Therefore, this trial requires timely detection, evaluation, and follow-up of laboratory alterations in selected liver laboratory parameters to ensure subjects' safety; see also section [5.2.6.1.4](#), adverse events of special interest.

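### The laboratory shift table uses only the last on-treatment value, so no described table counts subjects who were out of range at any time on treatment

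*SAP*

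**What the plan says.** On shifts against the reference range, SAP 7.8.2 has one rule: "Frequency tables of changes between baseline and last value on treatment with respect to the reference range will be presented by treatment". For the descriptive statistics over time, the same section says: "Descriptive statistics will be calculated by planned time point based on the worst value of the subject at that planned time point". Retests are handled there too: "unscheduled measurements will be assigned to the planned time point of the previous scheduled measurement".

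SAP 6.1 fixes what counts as a treatment for laboratory data, "Period R: Bupropion; Period T: BI + Bupropion", and what counts as on-treatment: "Measurements will be considered on-treatment, if they were taken within the on-treatment phases as defined in" Table 6.1: 1. In that table the bupropion phase of Period R ends 5 × 24 h after the dose. The last on-treatment phase of Period T ends 14 × 24 h after the last BI 1358894 dose.

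The Protocol Flow Charts place set B on Day 2 and Day 6 of Period R after dosing, and on Day -6, Day -1 and Day 6 of Period T. No set B is taken on Day -14 (footnote 16). Set C, which repeats the set B parameters, is taken at the end-of-trial examination, on Day 19 at the earliest.

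**The concern.** A shift table is where a reader looks to see how many subjects moved out of range on drug. Here it records where each subject stood at the end of the period. A subject in range at baseline whose ALT is high on Day -6 or Day -1 and normal at the last sample appears as normal to normal.

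Safety laboratory tests are a stated safety parameter (Protocol 2.2.1.2), and Protocol 1.4 notes that "this trial requires timely detection, evaluation, and follow-up of laboratory alterations in selected liver laboratory parameters". What is at stake is the tabulated frequency of transient abnormalities during BI 1358894 dosing, which this rule can only understate relative to a count over all on-treatment samples.

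**Working it through.** The SAP gives no figure for this table, so there is nothing to reproduce. The check places the samples in the analysis phases and applies the rule.

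**1. Sample times, in hours from the bupropion dose of the period** (Flow Charts; there is no Day 0)

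- Period T, set B: Day -6 = -144 h, Day -1 = -24 h, Day 6 = 120 h.
- Last BI 1358894 dose: Day 5 = 96 h, so the Day 6 sample follows it by 120 - 96 = 24 h.
- End of trial, set C: Day 19 = (19 - 1) × 24 = 432 h at the earliest.
- Period R, set B after dosing: Day 2 = 24 h, Day 6 = 120 h.

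**2. Phase limits** (SAP Table 6.1: 1)

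- Period R: 5 × 24 = 120 h, exactly the nominal Day 6 sample. Protocol 6.1 allows ±60 min for laboratory tests at that point, so the sample may fall on either side of the limit.
- Period T: 96 + 14 × 24 = 432 h, exactly the earliest nominal end-of-trial time. If that sample counts, the last on-treatment value is taken 336 h after the last dose. At the effective half-life of 50 to 70 h (Protocol 1.2.3), that is 336/70 = 4.8 to 336/50 = 6.7 half-lives.
- Parameters in set C but not in set B (electrolytes and glucose, for example) have no other scheduled sample after dosing. For them the 432 h tie decides whether any scheduled on-treatment value exists.

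**3. What the last-value rule shows**, for a subject in range at baseline. With k samples there are 2^k - 1 patterns with at least one abnormal value, and 2^(k-1) of them have an abnormal last value.

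| Case | k | Patterns with an abnormality | Shown as shift | Shown as no change |
|---|---|---|---|---|
| Period T, end of trial not counted | 3 | 7 | 4 | 3 |
| Period T, end of trial counted | 4 | 15 | 8 | 7 |
| Period R, Day 6 counted | 2 | 3 | 2 | 1 |
| Period R, Day 6 not counted | 1 | 1 | 1 | 0 |

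**4. Illustrations on assumptions that are not in the documents**

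- If an excursion lasts for one sample only and is equally likely at each, the Period T table shows it 1 time in 3, or 1 in 4 if end of trial counts.
- If each of three samples is independently abnormal with probability p in 18 subjects, the expected number shown as shifted per parameter is 18p by last value and 18[1 - (1 - p)³] by worst value.

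| p | Last value | Worst value |
|---|---|---|
| 2% | 0.36 | 1.06 |
| 5% | 0.90 | 2.57 |
| 10% | 1.80 | 4.88 |

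- One subject in 18 is 1/18 = 5.6 percentage points.

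**5. What a worst-value table does to the comparison of periods.** With no drug effect and p = 5%, two samples in Period R give 1 - 0.95² = 9.8% and three in Period T give 1 - 0.95³ = 14.3%. The last-value rule gives 5% in both.

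**The case against.** The strongest reply is that the report does not lose the abnormality. Descriptive statistics by time point include minimum and maximum (SAP 7), so a high ALT on Day -6 shows there. All individual values are listed with out-of-range ones highlighted, and possibly clinically significant values have their own listing. Findings judged clinically relevant become AEs and are counted in the AE tables, with AESIs tabulated separately. All of this stands. What remains uncovered is mainly the count of subjects with transient excursions that the investigator did not judge clinically relevant.

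A last-value table also answers a fair question, namely status at the end of exposure, and it is not affected by the unequal number of samples per period (step 5). That is a reason to keep it, not a reason to have nothing beside it. Nor can it be excluded that the sponsor's internal laboratory standard (SAP reference 9), which is not available here, adds a further display.

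Three stronger readings are tempting and should not be drawn:

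- *That SAP 7.8.2 contradicts itself by using worst values in one place and last values in another.* The worst-value rule chooses among a scheduled sample and its retests at one planned time point. The shift table chooses across visits. The two rules can stand together.
- *That a normal retest replaces the abnormal value, so the table is most misleading for subjects taken off treatment.* The SAP does not say whether its retest rule also governs the last time point in the shift table. If it does, the abnormal scheduled value at that time point would be kept. The text needs clarifying, but this mechanism is not established.
- *That the table fails the liver surveillance promised in Protocol 1.4.* That sentence concerns detection and follow-up while the trial runs, not a table in the report.

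**Conclusion.** The point holds in a limited form. For a completer, the two Period T samples taken during daily BI 1358894 dosing do not enter the shift table, and an excursion that has resolved by the last sample is counted as no change. No table described in the SAP counts subjects who were out of range at any time on treatment. This follows from the stated rule and the schedule alone.

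Its size cannot be fixed from the documents. The 1-in-3 detection share and the expected counts above rest on assumed excursion patterns. A reader might take from them that the table misses two thirds of transient abnormalities, but nothing in the documents supports that as an estimate.

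Severity is minor: this is a descriptive safety table in 18 healthy subjects, the individual values are all reported, and the PK conclusions are untouched. The ties at 120 h and 432 h are a separate small gap, because they leave open which sample is the last on-treatment one.

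**What to change.** In SAP 7.8.2:

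- Add a frequency table of shifts from baseline to the worst on-treatment value, using scheduled and unscheduled values, with highest and lowest shown separately where both directions matter. Keep the last-value table beside it.
- Show the number of on-treatment samples per subject and period, and note that worst-value frequencies are not directly comparable between periods. Period T has three scheduled set B samples (a fourth value if end of trial counts) against at most two in Period R.
- State whether a retest can be the last on-treatment value, or whether the worst value at that planned time point is used.
- State whether a sample at the 120 h limit in Period R, and an end-of-trial sample at the 432 h limit, counts as on-treatment.

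The cost is a few sentences in the SAP and routine programming, with no new data. Apart from the unequal sample numbers, the downside is that single spurious values become more visible. The listings can explain those.
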